3.3 Outcome measures/endpoints

To design and validate a 4-point assessment tool that can objectively measure the physical and psychological impact of complex surgical cases on a surgeon. The tool will then be taken forward and used in a large, multi-centre trial to determine whether a difference in surgeon impact exists between the different surgical modalities (open/laparoscopic/robotic) and if so to quantify the magnitude of the difference.

3.4 Primary endpoint/outcome

The proportion of cases where all the four components of the tool can be collected per case is the primary outcome.

3.5 Secondary endpoints/outcomes

- 1. Ergonomic analysis based on BMI including hip, waist ratio
- 2. Global measurements of surgeon including arm span, glove size and height to establish a potential association between ergonomics and anthropometric features of surgeon

4. TRIAL DESIGN

This is an observational study with the aim of investigating the impact that open and minimally invasive surgery (including robotic assist and straight stick laparoscopy) can have on surgeons' physical and psychological health.

The study will be using a monitoring tracking equipment called XSENS DOT Sensors, Actiheart heart rate monitor which are CE marked and will be used in its licensed indication. All equipment being used within the UHL operating theatres for the purpose of the study will have approval/authorisation from the medical physics department. The data collected will be downloaded on to a tablet using Bluetooth technology. Cortisol measurements were initially obtained at baseline (for each surgeon), preoperatively /intraoperatively (at time of the removal of specimen) and postoperatively as a biomarker to measure the cognitive impact of surgery. However, process evaluation within the feasibility stage has revealed it to be inconvenient and a potential disruption to theatre workflow especially if more than one case is recruited per list. The cortisol measurements obtained thus far will be included in the preliminary analysis but this biomarker will be omitted in the data collected at the validation stage. Surgeons will be expected to complete the STAI and modified Nordic WMS questionnaires as well. The WMS questionnaires have been further modified following the process evaluation carried out throughout the feasibility stage – to now include a numerical pain score to further objectively evaluate the intensity of the work related injuries sustained/ experienced.

XSENS DOT

ACTIHEART HEART RATE MONITOR

The research involves working in collaboration with the wearable robotics team at Loughborough University.

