3.2 Secondary objectives

- 1. Analysis to combine the 4 variables to give a single value of 'impact' (high/intermediate/low) per procedure
- 2. Validation of the combined impact values (subjective vs objective assessment)
- To analyse the impact of providing surgical training and supervision to surgical traineeswith varying levels of experience within a live surgical setting using heart rate monitoring as objective measures (if the case has been deemed suitable by the Consultant for the trainee)
- 4. Willingness of recruitment of patients/surgeons and sample size calculations for a future multi-centre study
- 5. Identification of primary/secondary outcomes for a future definitive multi-centre study

- 6. Optimisation/validation of patient data recording measures to capture anaesthetic/operative/clinical events and outcomes
- 7. Safety assessment of measurement tools and recording devices in the theatre environment
- 8. Optimisation of surgeon continuous heart rate monitoring during procedure, data collection and analysis
- 9. Optimisation of positioning and recording of muscle movement/activity sensors and streamlining of data-analysis
- 10. Optimisation/validation of WMS and State Trait Anxiety Inventory (STAI) questionnaires and data analysis
- 11. To include the analysis of the cortisol samples collected at the feasibility stage within the preliminary analysis

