10 STATISTICS AND DATA ANALYSIS

10.1 Sample size calculation

A key unknown for the feasibility of the full trial is whether it is possible to capture all 5 components of the tool for objective assessing stress of surgery therefore the proportion of surgeries with all 5 variables completely captured will be our primary feasibility outcome.

We believe this will be high, at around at least 90%. A sample size of 65 produces a two-sided 95% confidence interval with a width equal to 0.16 when the sample proportion is 0.90, with lower limit 0.80 and upper limit 0.96. This data will be used to determine the parameters to classify cases into low, intermediate and high impact depending on the physical/psychological impact on the surgeon.

A further 100 cases have been included as validation of the tool. This is based on a 50% prevalence of 'high' impact procedure and 95% confidence level and a sensitivity of 0.90 (0.772-0.970).

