10.3.2 Primary outcome analysis

Multi-variate analysis will be performed to identify factors increasing surgeon impact and statistical modelling will be used to calculate a single value that is representative of the cumulative 'impact' of the case on the surgeon so that cases can be categorised as 'high', 'intermediate' or 'low' impact. Case complexity (for example BMI, previous surgery) and subjective surgeon opinion will be compared with the impact classification to determine internal consistency (Cronbach alpha) and content validity.

Following the development of the impact classification, geographical external validation will be conducted at additional sites, and surgeons recruited to confirm the accuracy of the 5-point assessment tool.

Data gathered from the interviews will undergo qualitative analysis

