10.5 Procedure(s) to account for missing or spurious data

As this is a feasibility study looking at how feasible it is to collect this data, the trend of missing data i.e (which aspect is most frequently difficult to obtain) will be monitored. This will help understand whether or not all aspects of the tool are key to classifying the cases appropriately.

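### The instrument changed between development and validation, the protocol describes both a four- and a five-component tool, and nothing ties the cut-offs to items common to both stages

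*Protocol*

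**What the plan says.** **Source of the cut-offs.** Protocol 10.1, speaking of the 65 feasibility cases: "This data will be used to determine the parameters to classify cases into low, intermediate and high impact". A further 100 cases are there to validate the tool. Section 10.3.2 places that validation at additional sites, "to confirm the accuracy of the 5-point assessment tool".

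**What changed between the stages.** On cortisol, Section 4 says "this biomarker will be omitted in the data collected at the validation stage", and Section 8 confirms that no more swabs are taken. The results already obtained are kept; objective 11 in 3.2 reads "To include the analysis of the cortisol samples collected at the feasibility stage within the preliminary analysis". On the musculoskeletal (WMS) form, Section 4 says "The WMS questionnaires have been further modified following the process evaluation carried out throughout the feasibility stage", the change being "to now include a numerical pain score to further objectively evaluate the intensity of the work related injuries sustained/ experienced".

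**What the tool contains.** Sections 2 and 3.1 name heart rate, movement sensors, STAI and WMS. Objective 1 in 3.2 builds the impact value from four variables, and 3.3 and 3.4 also say four. The Aim in Section 3, the sample-size text in 10.1 and the validation sentence in 10.3.2 say five, and none of these three names the fifth.

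**How components are to be judged.** Section 10.5 will monitor which element is hardest to obtain and adds: "This will help understand whether or not all aspects of the tool are key to classifying the cases appropriately".

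**The concern.** External validation tests a tool only if the score and cut-offs fixed in the development data are applied unchanged to new cases. Here the development and validation cases carry different data, the text gives two answers on which variables form the score, and no sentence restricts the score to what both stages share.

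Two failures are possible. A rule that uses a variable absent at validation cannot be scored there. A rule that uses a variable absent at development has no cut-off to carry forward and would have to be fitted in the validation cases, which then no longer validate it. In either case, poor performance could not be separated from the change of instrument.

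The validation stage is 100 of 65 + 100 = 165 planned procedures (61%), and Section 2 names a validated tool as the study's product. The inference in 10.5 adds a further risk: a component could be judged dispensable because it is awkward to collect, when it may be the one that separates the categories.

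**Working it through.** **1. The plan's own figure.** Section 10.1 gives, for n = 65 and a proportion of 0.90, a 95% interval of 0.80 to 0.96 with width 0.16. The exact (Clopper-Pearson) limits are the beta quantiles B(0.025; x, n − x + 1) and B(0.975; x + 1, n − x). With x = 0.90 × 65 = 58.5 they are 0.800 and 0.960, width 0.160, so the figure is reproduced. It is the same whether four or five components make up full capture, so it cannot show which count is meant. The rest of the check is a comparison of the text.

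**2. Data available at each stage.**

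| Item | Feasibility (65) | Validation (100) |
|---|---|---|
| Heart rate, movement, STAI | yes | yes |
| WMS, earlier items | yes | yes, if retained (form not shown) |
| WMS pain score | only in cases done on the new form, number m not stated (0 to 65) | yes |
| Cortisol | some cases, number not stated | 0 |

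**3. If the five-component wording governs.** The fifth component is not named. Cortisol is the only measure that the protocol reports removing, so it is the natural candidate, but this is an inference. On that inference a five-component classification is computable in 0 of 100 validation cases.

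**4. If the four-component wording governs.** Cortisol is not an input, and its removal stops nothing. If the earlier WMS items were retained, a score built on them can be computed in all 100 validation cases, apart from ordinary missing data. What remains is the pain score: a WMS component that uses it can be calibrated only on m of the 65 development cases. The protocol does not say whether the pain score enters the component.

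**5. Section 10.5.** How often a component is missing estimates the chance of failing to collect it. Whether it is key to classification depends on how often the category changes when it is left out. Neither quantity determines the other: a component captured every time may be redundant, and one often missed may decide the category. The second quantity can be estimated from cases with everything captured. At the plan's 90% capture that is about 58 of 65 cases; 10.1 assumes this rate for all five variables, and if the four are among those five, four-variable capture is at least as high.

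**The case against.** The strongest reply is that the five is left over from before cortisol was removed. Sections 2 and 3.1 to 3.4 agree on four named components, objective 1 combines four variables, the list of data to be analysed in 10.3.1 omits cortisol, and objective 11 ties cortisol only to a preliminary analysis. The WMS change is described as an addition, so earlier items may still be scorable. Refining instruments between stages is what a feasibility study is for, and objectives 8 to 10 provide for it. The score is a secondary objective, and the choice of scored items can be left to an analysis plan.

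Much of this stands. A reader might infer that the developed tool cannot be scored in any validation case. The documents do not support that as a flat statement: nothing says cortisol enters the score, and on the four-variable reading it does not. A reader might also infer that all 65 feasibility cases lack the pain score; the protocol does not say when the new form came into use. Changing the form is not itself an error, and 10.5 says only that missingness will help, not that it alone decides which components stay.

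Three things survive. The five-component statements are current text, and they sit in the Aim and in the two statistical sections that define capture and validation. An analysis plan cannot follow both counts. The contradiction also reaches the primary outcome, since 10.1 defines full capture with five variables and 3.4 with four. And even as an aid, missingness carries no information on contribution to classification.

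**Conclusion.** The concern holds in conditional form. The data changed between development and validation, the protocol contradicts itself on the components, and it does not say that the cut-offs rest on items common to both stages.

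The size depends on the reading. With five components and cortisol as the fifth (an inference), 0 of 100 validation cases can be classified. With four components and the earlier WMS items retained (an assumption, since the form is not shown), the score can be computed at validation, and the exposure is limited to any use of the pain score, which is missing in 65 − m development cases with m not stated. The four-component reading has more support in the text, but nothing declares it to govern.

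This is more than missing detail. It should be settled before any validation case is scored, because a rule chosen after those data are seen is no longer independently validated. The 10.5 inference is unsound on either reading.

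**What to change.** - **Section 3 (Aim), 10.1 and 10.3.2:** replace five with the four named components: heart rate, movement, STAI and WMS.
- **10.3.2:** state that the score and cut-offs are derived from the feasibility cases using heart rate, movement, STAI and only those WMS items present on both form versions, and that they are locked before validation data are scored.
- **Cortisol:** keep it out of the score and use it only as an external comparator in the cases that have it. This still meets objective 11.
- **Pain score:** report it as exploratory until it has development data of its own.
- **10.5:** keep the pattern of missing data as a feasibility result. Judge the importance of a component by leaving each out in turn and counting how many complete cases change category.

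The cost is wording and one extra analysis, with no new data. The small downside is that the pain score does not contribute to the validated category.

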5. TRIAL SETTING

Surgeons will attend for a session (before the surgery takes place) with the research team to familiarise themselves with the equipment to be worn during the planned surgery to ensure this does not affect their technical abilities. The session will consist of the surgeon performing a series of standardised tasks on a laparoscopic simulator (LapAR Innovus) with and without the monitoring equipment to ensure that their surgical performance (as determined by objective measurements) is not impaired by wearing the equipment. They will also provide feedback on the contents of the questionnaires (WMS and STAI) and a semi-structured interview. The day will be arranged at the convenience of the surgeon. Refreshments will also be provided and they'll be available to take breaks when needed.

The study will be taking place at secondary care hospitals and will initially involve University Hospitals of Leicester NHS Trust and will expand to other sites within England at a later date. Additional sites that are added, will be added through the amendment process.

The study will be recruiting surgeons and patients within Gynaecology and Surgical Directorates.

Surgeons will be invited to participate by the research team.

Members of the study team are experienced in working in theatres and are also part of the clinical care team. During R&I processes, permission will be sought from the Clinical Management Group about the study and observations during operations. Theatres management team will also be made aware of the study and of the surgeon's involvement ahead of the operation.

On the day of the operation, members of the study team will take care to introduce themselves and request permission to observe the surgery. The Senior Theatre Nurse will be provided with evidence of informed consent and will be asked for confirmation of the patient's identity. At the start and end of the procedure, all the equipment that was used for the study will be signed in and out by two members of the research/clinical team. As part of this study, we will also ask the Surgeon to explain our presence to the wider theatre team and to ask if anyone has any objections. In the event that the case had been deemed suitable for the assisting trainee as per the Consultant (lead for the clinical team) we will then monitor their heart rate with their consent to analyse the impact of training on the trainer (Consultant Surgeon).

It will be detailed in the patient's medical records that they consented to the study as they will also be completing a separate consent form. Patient measurements (waist/hip) will be taken on the morning of surgery.

The sensors will be safety assessed by the medical physics team at the hospital before being used by the surgeons in the theatre setting.

6. PARTICIPANT ELIGIBILITY CRITERIA

The study involves 2 cohorts: surgeons and patients.

6.1 Inclusion criteria

Surgeons:

- Consultant Surgeons and Gynaecologists
- Able to consent
- Patient consents to their surgeon participating in the study

Patients:

- All patients
- Able to consent
- Undergoing intra-abdominal surgery with a procedure expected to last less than 2 hours in duration
- >18 years

6.2 Exclusion criteria

Surgeons:

Besides the inverse of the inclusion criteria, patients who do not consent for their surgeon to participate.

Patients:

Inverse of the inclusion criteria.

7. TRIAL PROCEDURES

Schedule of Procedures

Procedures	Visits (insert visit numbers as appropriate			Visits (insert visit numbers as appropriate)			
	Screening	Baseline	Visit 1 (before the operation)	Pre- Op	During Op	After Op	Follow Up & post interview
Surgeons:							
Approached by Research team	х						
Informed consent		Х					
Attendance at Leicester University			х				

 Monitoring of the equipment Laparoscopic simulator tasks Feedback on questionnaires Semi structured interview 						
Subjective assessment about the complexity of the procedure					Х	
Sensor monitoring				х		
Pre-op questionnaire			х			
Post-op questionnaire					х	
Interview						X2
Patients:						
Eligibility check	х					
Informed consent		х				
Information collected from medical records		х	х		х	

7.1 Recruitment

Surgeons

An email invite attaching the PIS will be circulated to the surgeons by the Research Team at the hospital site. Surgeons who wish to participate can then contact the research team (who are also part of the clinical care team) to discuss the study further and for consent to take place.

Patients

Surgeons will be given an eligibility criteria list to decide which patients should be invited to participate in the study. Patients will be provided with the PIS at one of the routine appointments by their clinical care team. The patient will also have at least 24 hours to decide if they wish to take part or not. The researcher will also be available to answer any queries. They will need to contact the research team to let them know if they wish to participate. The researcher will consent the patient to study on the day of the operation. All due care will be taken into consideration to ensure that the consenting process does not coincide or interrupt clinical care on the day of the operation.

7.1.1 Participant identification

The research team will not be identifying patients, this will be conducted by the direct clinical care team.

7.1.2 Screening

The surgeons will be screening suitable patients.

7.1.3 Payment

No payments will be made to participants since no additional visits will be required.

7.2 Consent

Prior to participation in the study, participants (surgeons and patients) will be required to give written informed consent.

Consent will be required from the patient in order for the surgeon to participate in the study.

Consent will be taken on the day of the surgery by a member of staff from the research team. All due consideration will be taken to ensure that the consent process does not coincide with the clinical day to day activities on the ward.

Written and verbal versions of the participant information and informed consent will be presented to the participants detailing no less than: the exact nature of the study; the implications and constraints of the protocol; the known side effects and any risks involved in taking part. It will be clearly stated that the participant is free to withdraw from the study at any time for any reason without prejudice to future care, and with no obligation to give the reason for withdrawal.

The participant will be given sufficient time to consider the information leaflets, and the opportunity to question the Investigator, their GP or other independent parties to decide whether they will participate in the study. They will be allowed, at least 24 hours to make their decision. Written Informed Consent will then be obtained by means of participant dated signature and dated signature of the person who presented and obtained the informed consent. The person who obtained the consent must be suitably qualified and experienced, and have been authorized to do so by the Chief/Principal Investigator as detailed on the Delegation of Authority and Signature log for the study. The original signed form will be retained at the study site within the Trial Master File (TMF) or Investigator Site File (ISF). A copy of the signed Informed Consent will be given to participants and a copy retained in the participant medical notes.

Patient information sheets, consent forms and any amendments will be approved by Research Ethics Committee (REC), Health Research Authority (HRA), Study Sponsor and the local trust R&I department prior to implementation. The process of consent requires individual discussion with the participants.

7.3 Randomisation

N/A

7.4 Blinding

N/A

7.5 Unblinding

N/A

ISSUE Protocol Version v5 24.09.2022

7.6 Trial assessments/procedures

Surgeons

Pre-study assessment will be conducted as detailed in section 5 prior to surgery.

The LapAR (Inovus) comes with its own established system of data capture and analysis that provides objective and comparable metrics when the surgeon undertakes different simulated tasks. The software will include both general surgical and gynaecological relevant exercises. The data obtained will be used to establish that the sensors and heart rate monitor will not have a negative impact on the surgical tasks itself in the live setting.

Day of surgery

A member of research team will meet with the surgeon (this will be arranged in advanced so that it does not coincide with clinical processes) for the following assessments:

Before surgery:

- Completion of the questionnaire which will take about 10 minutes to complete
- Wearing of sensors

After surgery:

Completion of the questionnaire which will take about 10 minutes to complete

Surgeons will be invited to participate in an interview with the researcher to discuss their experience of the measurement tool and challenges they have experienced when collecting the data. This will be two interviews per participant to gather their views on the various aspects of the study as a whole as well as their potential ongoing musculoskeletal symptoms.

Patients

Access to medical records to obtain data:

- Medical co-morbidities
- Body habitus (BMI)
- Intra/post-operative events/recovery
- Waist/hip measurements will be taken by the researcher on the morning of surgery.
- Subjective assessment from the patient's healthcare professional regarding the level of complexity of the procedure.

There are no research trial specific assessments for patients but consent will be sought to access their medical records to obtain data from their medical records. The data collected will be pseudonymised at the site before being transferred to the University of Leicester. There will be no personal data being transferred.

